5.6.2 Replacements

In all cases of early withdrawal from study, a replacement participant may be enrolled.

6 STUDY PROCEDURES

6.1 Summary of Procedures

Table 1. Schedule of Study Procedures and Assessments

	Screening	Study Intervention (Weeks 1-3)	Study Intervention (Week 4)	Study Intervention (Weeks 5-7)	Study Intervention (Week 8)	Taper/Bridge	Follow-Up	Early Withdrawal/ Discontinuation
	Day -29 to 0 ¹	Day 1 ¹⁻²¹ (± 1 day)	Day 22-28 (± 3 days)	Day 29-49 (± 1 day)	Day 50-56 (± 3 days)		5 (+ 2) days post final study dose	
Informed consent/assent	X							
Distribution of device for remote HR and BP assessment		X ³						
Demographics	X							
Medical History	X							
Physical Exam	X	X ³						
Weight/height			X		X			
Vital Signs	X	X ³	X		X			
Concomitant Medications of Interest	X		X		X			
ECG	X		X		X			X
Lab assessments	X		X ¹¹					
Pregnancy test ¹³	X							
Blood Collection for PK			X ²		X ²			X ²
Randomization		X ³						
Dose escalation with HR and BP assessment		X ⁴	X ⁴	X ⁴				
Study product administration		X ⁵	X	X	X			
Unmasking					X			X
Study drug taper/bridge						X ⁶		X
Study Diary			Continuous			X ⁶	X ⁶	
CGI-S	X							
CGI-I		X ⁷	X	X ⁷	X			X
ABC	X		X		X			X
asQ Tool ¹²	X		X		X			
Sleep assessments		X ³	X		X			
Safety Events ⁸	X ⁹	X	X	X	X	X	X ¹⁰	X

1 – Day 0 and Day 1 may be the same calendar day.

2 – Preferred sampling: within 60 minutes prior to study product dose or 30-120 minutes after study product dose.

3 – Randomization; distribution of device for remote HR and BP assessment; physical exam, including weight/height; vital signs; and sleep assessments occur only on Day 1 prior to study product administration.

4 – Just prior to dose escalation time point, every 5 (+ 2) days, parent/legal guardian will be asked to measure HR and BP.

5 – Initial dose occurs on Day 1, Day 0 and Day 1 may be the same calendar day. The initial dose will be administered before bedtime on Day 1. Subsequent doses occur according to Section [6.13.1](#).

6 – For GIR arm only. Participants who choose to discontinue GIR will be tapered off study drug at 1 mg every 3 days. Participants who choose to transition to standard of care GIR will continue on up to 7 days of study drug to bridge to standard of care GIR. See Section [6.13.2](#).

7 – Weekly CGI-I, beginning at first weekly telephone assessment.

8 – Includes AEs, SAEs, and safety ESIs, as described in Section [7.1.2](#).

9 – Only AEs directly related to study procedures (e.g., blood collection) during the screening period will be collected.

10 – A final Telephone Safety Assessment, including all safety events, will occur at 5 (+ 2) days after final study product administration.

11 – In the rare event that blood cannot be collected for any reason at Week 4, blood for LFTs can be collected at the Week 8 visit.

12 – Only used in participants ≥ 8 years old, as described in Section [6.10](#).

13 – For participants who have reached menarche only, either urine or blood test is acceptable.

6.2 Screening (Day -29 to 0)

The investigator will screen participants in accordance with the eligibility criteria detailed previously (Section 5.2). The investigator will not exercise selectivity so that bias is prevented.

The following assessments/procedures will occur during the Screening period:

- Informed consent/assent
- Demographics, including identified gender, race, ethnicity, and date of birth
- Complete Medical history
- Physical exam, including weight and height
- Vital signs, including BP and HR
- Concomitant medications of interest
- ECG
- Lab assessments for baseline complete blood count (CBC) w/differential, basic metabolic panel (BMP), liver function tests (LFTs), Thyroid function studies (Thyroid Stimulating Hormone [TSH], free T4)
- For participants who have reached menarche only, pregnancy test (urine or blood test is acceptable)
- CGI-S for Eligibility (Section 6.9.3)
- ABC for Eligibility (Section 0)
- asQ for Eligibility, as appropriate, for participants \geq 8 years old who do not have prior known suicidality (Section 6.10)
- AEs directly related to study procedures

6.3 Study Intervention (Day 1 to 56 \pm 3 days)

Day 1 (Day 0 and Day 1 may be the same calendar day):

- Randomization
- Physical exam, including weight and height
- Vital signs, including BP and HR
- Study product administration – single dose at bedtime on Day 1
- Study Diary completion training and provision
- Safety Events, including AEs, SAEs, and safety ESIs; collection of safety events will be initiated after the first study product administration
- Parent/legal guardian-completed sleep assessments (Section 6.9.2)

Weeks 1-3 (Day 1-21 \pm 1 day):

- Study-product administration
- Dose escalation with BP and HR assessment (Section 6.8), prior to dose escalation time point, every 5 (+ 2) days.
- Safety Events, including AEs, SAEs, and safety ESIs

- Study Diary review
- Clinician completed weekly CGI-I, beginning at first weekly telephone assessment (approximately Day 5) (Section **6.9.3**)

Week 4 (Day 22-28 ± 3 days):

- Concomitant medications of interest
- Weight/height
- Vital signs, including HR and BP
- ECG
- Lab assessments for liver toxicity: LFTs
- Blood Collection for PK
- Dose-escalation assessment (Section **6.8**)
- Study-product administration
- Study Diary review
- Clinician-completed CGI-I (Section **6.9.3**)
- Parent/legal guardian-completed ABC (Section **0**)
- Parent/legal guardian-completed sleep assessments (Section **6.9.2**)
- asQ, as appropriate, for participants ≥ 8 years old (Section **6.10**)
- Safety Events, including AEs, SAEs, and safety ESIs

Weeks 5-7 (Day 29-49 ± 1 day):

- Dose-escalation with BP and HR assessment (Section **6.8**), prior to dose escalation time point, every 5 (+ 2) days
- Study-product administration
- Study Diary review
- Clinician-completed weekly CGI-I (Section **6.9.3**)
- Safety Events, including AEs, SAEs, and safety ESIs

Week 8 (Day 50-56 ± 3 days):

- Weight/height
- Vital signs, including HR and BP
- Concomitant medications of interest
- ECG
- Lab assessments for liver toxicity: LFTs, *only if unable to collect at the Week 4 visit*
- Blood Collection for PK
- Study-product administration
- Study Diary review

- Clinician-completed CGI-I (Section [6.9.3](#))
- Parent/legal guardian-completed ABC (Section [0](#))
- Parent/legal guardian-completed sleep assessments (Section [6.9.2](#))
- asQ, as appropriate, for participants \geq 8 years old (Section [6.10](#))
- Safety Events, including AEs, SAEs, and safety ESIs
- Unmasking of participant to determine standard of care plan

6.4 GIR Taper/Bridge (Up to 6 days post last study product administration)

Procedures will vary for those participants who are randomized to receive study drug, depending on their decision for GIR treatment following unmasking.

- Participants randomized to receive study drug, who choose to discontinue GIR:
 - See Dose Discontinuation/Taper (Section [6.13.2](#))
 - Study Diary completion
- Participants randomized to receive study drug, who choose to transition to open-label GIR per standard of care:
 - Participants will have enough study product to allow for a 7-day bridge of manufactured GIR and will be instructed to contact their healthcare provider in order to obtain a clinical prescription of GIR within 7 days.
 - Study Diary completion

Note: Participants randomized to receive placebo will proceed directly to the Telephone Safety Follow-up (Section [6.5](#))

6.5 Telephone Safety Follow-up (5 + 2 days after final study product administration)

A Telephone Safety Assessment, including a Study Diary review will be conducted for all participants, at 5 (+2) days after final study-provided product administration.

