		
Updated definition of asQ from Ask-Suicidal-Screening Questions to Ask Suicide-Screening Questions.
 
Updated to indicate contraception is allowed but not required.
 
Specific references to pharmacy or pharmacist were removed and kept vague as site or clarified as pharmacist (or designee).
 
Changed concomitant medications to concomitant medications of interest.
 
Changed Study Product Diary to Study Diary since HR/BP was added to it.
 
Updated the definition of the efficacy population.
 
References and TOC were updated accordingly.

--	--	---

[figure not shown]
PROTOCOL SYNOPSIS

Protocol Title:	Guanfacine for Hyperactivity in Children with Down Syndrome (HYPEbeGONE_DS)
NCT #:	06042257
Phase:	Phase 2
Study Product(s) or Intervention:	Guanfacine hydrochloride, Immediate Release
Objectives:	
Primary:
 
1. Determine efficacy of guanfacine immediate release (GIR) for the treatment of hyperactivity/impulsivity and inattention in children with Down syndrome (DS) after 8 weeks of treatment. 
Secondary:
 
1. Characterize the safety profile of GIR in children with DS. 
Exploratory:
 
1. Characterize GIR exposure in children with DS.2. Characterize the exposure-response relationship of GIR for the treatment of hyperactivity/impulsivity, inattention, and sleep quality in children with DS.
Study Design:	Prospective, multi-center, randomized, double-masked, placebo-controlled, flexibly-dosed trial
Study Population:	Children ages 6-12 years old with DS

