4.4 Duration of Participant Participation

Participants will undergo a screening period of up to 29 days. Eligible participants will receive GIR for up to 8 weeks plus a bridge or taper period, or placebo for up to 8 weeks. The treatment period will consist of study product administration from day 0 through day 56 with a masked dose-escalation period from day 0 through day 49. Unmasking of participant and site staff will occur after the week 8, in-person assessment, Day 56 (\pm 3 days).

After unmasking, participants who were randomized to receive placebo will have a final telephone safety assessment 5 (+ 2) days after final study dose is administered.

After unmasking, participants who were randomized to receive GIR will be given the option to 1) remain on GIR and to transition to open-label GIR per standard of care or 2) taper off of GIR. If the participant, in consultation with their clinical provider, chooses to remain on open-label GIR via standard of care, participants will have enough study product to allow for a 7-day bridge of manufactured GIR study drug to allow time to receive the routine clinical prescription of non-study provided GIR. A final telephone safety assessment will occur 5 (+ 2) days after final manufactured GIR study dose is administered. Alternatively, if the participant, in consultation with their clinical provider, chooses to discontinue GIR, a manufactured GIR taper will be instructed to proceed by a decrease of 1 mg every 3 days (maximum 6 day duration, depending on final study dose) to minimize rebound hypertension. A final telephone safety assessment will occur 5 (+ 2) days after the final manufactured GIR study dose is administered.

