6.8 Dose Escalation Assessments

Every 5 (+ 2) days through Week 7, just prior to each dose escalation assessment, parent/legal guardian will be asked to measure HR and BP using the device given to them from the study team at the time of randomization. A telephone or in-person assessment by the treating clinician will occur to determine dose escalation. If the participant reaches the maximum dose of 3 mg/day, prior to Week 7, no dose escalation will occur. Alternatively, a CGI-I will be determined by the treating clinician and any score of 3 or worse (higher) will warrant dose escalation, provided no significant safety concerns exist. AEs and safety ESIs will be recorded to assess safety.

Clinically significant findings that would prevent dose escalation include, but are not limited to:

- CGI-I score of 2 or 1
- HR and BP values that are considered unsafe to dose escalate:
 - Clinically significant hypotension, defined as systolic BP percentile less than the 5th percentile.^{31,34} This corresponds to systolic BP percentiles for neurotypical children under the 8th percentile for males and under the 10th percentile for females.
 - Clinically significant bradycardia, defined as HR > 2 SD below mean for age
- Any AEs or safety ESIs that make it unsafe to dose escalate, at the discretion of the treating clinician
- Any other finding that indicates it is not safe to dose escalate, at the discretion of the treating physician and/or principal investigator (PI).

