6.13.2 Dose Discontinuation /Taper

If a participant randomized to receive GIR withdraws from study early or chooses not to continue treatment with GIR via standard of care at the end of Week 8 unmasking, a drug taper plan will be employed for all participants whose final drug dose is > 1 mg/day. The dose taper will be a decrease in increments of 1 mg every 3 days. The taper will last a maximum of 6 days, but may be shorter if starting taper dose is less than 3 mg/day. Study Diary will be completed during the discontinuation/taper period.

Participants receiving < 1 mg at the final study drug administration will stop study drug treatment and will follow procedures for early withdrawal/termination (as applicable) or will proceed to Telephone Safety Follow-up (Section [6.5](#)).

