7.1.2 Safety Events of Special Interest (ESIs)

A safety ESI is a select safety event that could be related to the study drug. Safety ESIs will be solicited for their occurrence (No or Yes) at weekly dose-escalation assessments, including in-person assessments (Week 4 and Week 8), and the final telephone safety assessment (5 + 2 days) after the final dose of study drug. The safety ESIs documented will be assessed by the investigator/delegate (defined as a clinician licensed to make a diagnosis) for intensity, causality, and association to provide uniform data collection of all events. Any reported ESIs should be managed, as needed, according to clinical judgement and local guidelines.

Safety ESIs include:

- Syncope/passing out
- Sedation
- Trouble falling asleep
- Trouble staying asleep
- Trouble waking up
- Drowsiness
- Decreased Energy/Fatigue
- Trouble concentrating
- Trouble breathing
- Constipation
- Diarrhea
- Nausea
- Vomiting
- Skin rash
- Itching
- Change in appetite
- Anxious/fearful

- Sadness/depressed mood
- Self-injurious behavior
- Clinically significant hypotension, defined as systolic BP percentile less than the 5th percentile.^{31,34} This corresponds to systolic BP percentiles for neurotypical children under the 8th percentile for males and under the 10th percentile for females.
- Clinically significant bradycardia, defined as HR > 2 SD below mean for age

The following safety ESIs will only be assessed at in-person visits (Week 4 and Week 8):

- Any clinically significant cardiac event (e.g., clinically significant changes on ECG)
- Suicidality via the asQ Tool (see Section [6.10](#))

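### The taper is meant to limit rebound hypertension, but the protocol text requests no blood pressure reading during or after it and does not solicit raised blood pressure

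*Combined protocol and SAP*

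**What the plan says.** **The hazard.** Section 4.4 sets a taper of 1 mg every 3 days, for at most 6 days, "depending on final study dose) to minimize rebound hypertension". Section 6.13.2 applies it to GIR children whose final dose is above 1 mg/day, both at early withdrawal and after the Week 8 unmasking.

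**When BP is requested.** Table 1 and Sections 6.2 and 6.3 place clinic vital signs at Screening, Day 1, Week 4 and Week 8. Home readings are tied to dose escalation. Table 1 note 4 says: "Just prior to dose escalation time point, every 5 (+ 2) days, parent/legal guardian will be asked to measure HR and BP". Section 6.8 gives the end of that schedule: "Every 5 (+ 2) days through Week 7, just prior to each dose escalation assessment".

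**What happens after stopping.** Section 6.4 lists only the taper or bridge itself and the diary. Section 6.13.2 adds: "Study Diary will be completed during the discontinuation/taper period". Section 6.5 sets the last contact, 5 (+2) days after the last study-supplied dose: "A Telephone Safety Assessment, including a Study Diary review will be conducted for all participants". The v3.0 entry in the change history explains that the diary was renamed "since HR/BP was added to it".

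**Early withdrawal.** Sections 5.5.2, 5.6.1 and 6.6 list an ECG, a PK sample, the ABC and the CGI-I, and 6.6 adds safety events. None of them lists BP.

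**What is solicited.** Section 7.1.2 asks about events of special interest (ESIs) at the escalation assessments, the in-person visits "and the final telephone safety assessment (5 + 2 days) after the final dose of study drug". The list has low BP and low heart rate, but not raised BP.

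**The concern.** BP is followed closely while the dose goes up, when the expected effect is a fall. The hazard named for stopping is a rise, and the written schedule of readings ends before withdrawal begins. The solicited list also looks in the on-treatment direction only.

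A rise without symptoms can be found only with a cuff. Parental observation is a weak substitute here, because Section 14.2 anticipates that some participants will be nonverbal or minimally verbal. Section 2.1.1 notes that BP in children with Down syndrome tends to run lower than in age-matched controls, so a reading taken on drug just before the taper would be a useful comparator. A child who stops early has no such reading listed at the withdrawal visit.

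What is at stake is the safety description of stopping GIR and the care of individual children at home. The efficacy results are not at stake.

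**Working it through.** **Inputs**
- Taper: 1 mg less every 3 days if the final dose exceeds 1 mg/day (6.13.2); dose levels 0.5 to 3.0 mg/day (Table 3).
- Final call: 5 to 7 days after the last study-supplied dose (6.5).
- Last BP for a child who completes treatment: the Week 8 visit (6.3).
- Assumption: the taper starts at the Week 8 visit.
- Assumption: exactly 1 mg/day means no taper. Section 6.13.2 covers doses above and below 1 mg but does not assign 1 mg itself.

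**Reproducing the plan's 6-day maximum.** From 3 mg/day: 3 days at 2 mg, then 3 days at 1 mg, then off. That is 2 × 3 = 6 days, as stated.

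**Interval from the Week 8 BP to the final call** = taper days + 5 to taper days + 7. **Added readings under the fix** = taper steps + 1.

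| Final dose (mg/day) | Dose path | Taper days | Week 8 BP to call (days) | Added readings |
|---|---|---|---|---|
| 3.0 | 2.0, 1.0, off | 6 | 11–13 | 3 |
| 2.5 | 1.5, 0.5, off | 6 | 11–13 | 3 |
| 2.0 | 1.0, off | 3 | 8–10 | 2 |
| 1.5 | 0.5, off | 3 | 8–10 | 2 |
| 1.0 or 0.5 | off | 0 | 5–7 | 1 |

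For a child who tapers, the interval contains the whole withdrawal: every taper step and the first 5–7 days off drug.

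**Early stoppers.** The last BP is the latest of the Day 1 vital signs, an escalation reading and the Week 4 vital signs. The documents do not fix how old that reading is when the taper starts, so no single interval can be given.

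**How many children.** The GIR arm is about 60 × 2/3 = 40. Those who discontinue are an unknown part of it. Their final doses are also unknown: Section 10.6 cites a mean of 1.1 mg/day in the earlier open-label Down syndrome study, and a modal 3 mg/day of the extended-release form in the autism trial.

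**The case against.** **The diary may already do this.** It has HR/BP entries, GIR families keep it through taper or bridge, they hold the device, and staff review it at the final call. Version 3.0 both renamed the diary and clarified its use in this period, so the extension may have been deliberate. This is the strongest counter-argument, and it limits the point to the protocol text. It does not remove the point: a diary gives a place to write a value, while every written instruction to measure at home is tied to escalation.

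**Other safeguards exist.** The taper is itself the control for rebound. Sections 7.1 and 7.5 make a clinically significant change reportable through 5 (+2) days after the last dose. Section 5.6.1 requires follow-up of children stopped for an adverse event. All of this stands, so the gap is in measuring and asking, not in reporting. A reader might infer that rebound would escape safety reporting altogether; the documents do not support that.

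**Stronger readings that do not hold**
- *Low-BP and low-heart-rate answers at the final call are unsupported in both arms.* For placebo children and GIR children without a taper, the Week 8 reading is 5–7 days old. That matches the plan's own home-reading interval of 5 (+2) days.
- *Every GIR child is off drug for 5–7 days before the call.* Bridging children are meant to continue on prescribed GIR, and their call is timed from the last study-supplied dose.
- *Bridging children may run out and stop abruptly.* Section 6.4 says families "will be instructed to contact their healthcare provider in order to obtain a clinical prescription of GIR within 7 days". The documents give no rate of failure, and continuity of supply is a separate matter.

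**Conclusion.** The point holds for the protocol text. The plan names rebound hypertension as the reason for the taper, yet it requests no BP during or after the taper, lists none at early withdrawal, and does not solicit raised BP.

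For GIR children who stop after Week 8, the last listed reading precedes the final call by 5–7, 8–10 or 11–13 days according to final dose. These figures rest on the taper starting at the Week 8 visit and on no taper at exactly 1 mg/day. They are elapsed days, not a measure of risk: the documents give no frequency, timing or severity for rebound, and Section 2.4.2 does not list it among the drug's risks. The number affected is an unknown subset of about 40.

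A reader might go further and conclude that no readings will be taken. That cannot be said, because the diary form and MOP are not in the documents.

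This is a cheap improvement to safety monitoring. The primary endpoint, the secondary efficacy endpoints and the safety endpoint through Week 8 are unaffected.

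**What to change.** 1. In Table 1 and Sections 6.4, 6.5 and 6.13.2, for GIR children who discontinue (after Week 8 or early), request a home HR/BP reading at each taper step and one before the final call, recorded in the existing diary.
2. In Table 1 and Sections 5.6.1 and 6.6, list BP at the in-person Early Withdrawal visit. It serves as a baseline before the taper and supports the low-BP event collected there; it would not itself detect rebound.
3. In Section 7.1.2, add clinically significant raised BP to the solicited events. The threshold, and the action on a high reading, are for the sponsor's clinicians.
4. If the diary form or MOP already asks for these readings, say so in the protocol; items 2 and 3 would still apply.

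No added reading is needed for placebo or bridging children.

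**Cost.** One to three home readings per discontinuing GIR child (3 at 2.5–3 mg/day, 2 at 1.5–2 mg/day, 1 with no taper), on a device the family already has; one BP at an in-person Early Withdrawal visit; and one more solicited item. Sample size, masking during treatment and the efficacy analysis stay as they are.

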6.6 Early Withdrawal / Termination Visit

If a participant withdraws from study product administration or terminates from the study early, the study team will attempt to collect the following at an in-person visit, if an in-person visit is not feasible, a telephone assessment will occur to obtain the following assessments/procedures:

- Safety Events, including AEs, SAEs, and safety ESIs
- ECG (in-person only)
- Parent/legal guardian-completed ABC (Section [0](#))
- Clinician-completed CGI-I (Section [6.9.3](#))
- Blood collection for PK analysis (in-person only)
- Unmasking of participant and manage GIR Taper/Bridge per Section [6.4](#). Unmasking should only occur following completion of the other Early Withdrawal / Termination Visit Assessments above.

